3.1.1 Enrollment Phase

Clinicians and Parents Participating in Co-design of the intervention

Potential clinician subjects and parents of previously hospitalized patients will be screened using the protocol inclusion and exclusion criteria. Clinicians will be recruited into the study through an open announcement of the study by the study team at faculty meetings and via a faculty listserv that will give them contact information to follow up with a study team member if they are interested in participating (See Appendix 11.1 for recruitment email). Approximately 15 clinicians will be enrolled for the co-design. Parents will be approached via a Family Advisory Council invitation and email listserve call. Approximately 5 parents of previous patients who have been admitted to the ICU will be enrolled.

Clinicians Participating in Intervention

Potential clinician subjects will be screened using the protocol inclusion and exclusion criteria. CICU clinicians will be recruited into the study through an open announcement of the study by the study team at faculty meetings and via a faculty listserv that will give them contact information to follow up with a study team member if they are interested in

participating (See Appendix 11.2 for recruitment email). The goal for enrollment will be at least 20 CICU clinicians.

Clinicians Not Participating in Intervention

Clinician team members participating in an observed family meeting who will not undergo the CST (because they were not eligible, did not wish to participate in the study, or were not approached because sufficient clinicians were already enrolled) will be consented to being audio or video recorded and completing a survey before the scheduled family meeting.

Parent-patient Dyads Participating Prior to Intervention

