3.1.5 Follow-Up Phase

Clinicians Participating in Intervention: After CST, a set of actual family meeting encounters with these trained clinicians will be audio recorded and coded, ensuring there are 23 meetings with each category of person trained. We estimate a total of 28 meetings will need to be recorded in order to obtain 23 meetings with each discipline. Clinicians participating in the intervention will complete an online survey after the actual family meeting that they are observed participating in.

This survey will measure team member perception and satisfaction with collaboration. We will administer the modified Baggs CSACD-N tool to all clinician team members who participate in an actual encounter, which will capture each discipline's experience with collaboration with other team members and satisfaction with care decisions.

Clinicians Not Participating in Intervention: Consented non-participating clinicians will have their normal, scheduled family meetings. Actual family meeting encounters with these clinicians will be audio or video recorded and coded. Clinicians not participating in the intervention will complete the same online survey as those clinicians participating in the intervention after the observed actual family meeting.

Parent-patient Dyads Participating in the Survey or Interview After Intervention: Potential subjects will be screened using the protocol inclusion and exclusion criteria. Parent-patient dyads will be recruited into the study in person, over the phone, or via e-mail. The goal for enrollment will be up to 50 parent-patient dyads, with 30 evaluable parent-

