3.4.2 Clinicians Participating in Intervention

3.4.2.1 Inclusion Criteria

- Pediatric CICU clinicians (attending intensivists, cardiologists, cardiac surgeons, front line clinicians, nurses, and social workers) at CHOP who volunteer to undergo communication skills training.

3.4.2.2 *Exclusion Criteria*

- Clinicians who will not participate in CHOP's CICU chronic care meeting in the following year.

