Team function will be analyzed for simulated family meetings by comparing the change in the number of minutes that clinicians from each discipline speak in pre and post-CST meetings using linear regression and controlling for the length of the meetings.

To assess the impact of the CST program in actual family meetings, audio recordings from actual family meetings will be coded and compared to coded audio recordings from pre-intervention actual family meetings. Since there are generally at least 2 clinicians in each team encounter, we will examine the individual skill acquisition within each part of the team encounter. Within each discipline, there are several clinicians involved in multiple team meetings. We will use fixed-effects regression with a clinician identifier variable as a covariate so that we can examine the effect of CST intervention on skill acquisition, adjusting for the effects of individual clinicians.

Team function will be analyzed in the same way as in simulated meetings by comparing the change in the number of minutes that clinicians from each discipline speak in pre and post-CST meetings using linear regression and controlling for the length of the meetings.

The difference in team member perception and satisfaction with collaboration will be measured after their participation in clinical encounters both pre and post-CST by administering the modified Baggs CSACD-N tool to all clinician team members who participate in an actual encounter. This tool will capture each discipline's experience with collaboration with other team members and satisfaction with care decisions. Means and standard deviations will be calculated for the tool and t-tests will determine if there are significant differences for each discipline pre and post-CST.

Hypotheses will be tested using logistic regression modeling with significance of the two-tailed hypothesis tests set at alpha equal to 0.05.

Clinician perception of the usefulness of CST and satisfaction with the training will be identified by descriptive statistics and differences in the mean and median scores will be calculated to determine retention in perceptions of usefulness one month after the training.

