6.4 Sample Size and Power

We hypothesize that the CST will change clinician behavior by increasing the number of skills demonstrated in a simulated family meeting. Sample size calculations using existing data about acquisition of skills being evaluated in the CST²⁹ demonstrated that a total of 20

clinicians will be needed to identify significant changes in the following skill outcomes: discussing the big picture, responding to emotion, and performing several empathetic verbal skills using 80% power and an alpha=0.05.

Sample size calculations for determining change in clinician skill acquisition by discipline requires that there be an adequate number of actual encounters recorded such that they can be analyzed by provider type. Sample size calculations for simulated family meetings apply here as well in that we will need to have at least 20 team encounters pre and post-CST intervention to be able to look at the change in outcome before and after the intervention. Since there are generally at least 2 clinicians in each team encounter, we will examine the individual skill acquisition within each part of the team encounter. Within each discipline, there are several clinicians involved in multiple team meetings. We will use fixed-effects regression with a clinician identifier variable as a covariate so that we can examine the effect of CST intervention on skill acquisition, adjusting for the effects of individual clinicians.

Team function will be analyzed by comparing the change in the number of minutes that clinicians from each discipline speak in pre and post-CST meetings using linear regression and controlling for the length of the meetings. Sample size calculations based on previous data⁸⁷ and assuming 80% power and an alpha=0.05 will only require 3 paired respondents pre and post-CST to identify significant differences.

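### If binary skills are analysed by logistic regression with a clinician identifier as covariate, the training effect is overstated by about 10–30% on the log odds scale at the Protocol's meeting counts

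*Protocol*

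**What the plan says.** Protocol 6.3.2 gives the model for skill acquisition in actual meetings: "We will use fixed-effects regression with a clinician identifier variable as a covariate". Section 6.4 repeats it and gives the purpose as "adjusting for the effects of individual clinicians". The stated reason is repeated attendance: "Within each discipline, there are several clinicians involved in multiple team meetings". Later in 6.3.2 a general sentence reads: "Hypotheses will be tested using logistic regression modeling with significance of the two-tailed hypothesis tests set at alpha equal to 0.05". Neither section names the link function of the fixed-effects model, says whether clinician effects are estimated or conditioned out, or names the test statistic.

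On scale, Protocol 3.1.1 says "The goal for enrollment will be at least 20 CICU clinicians", drawn from six categories in 3.4.2.1: "attending intensivists, cardiologists, cardiac surgeons, front line clinicians, nurses, and social workers". Section 3.1.5 says "We estimate a total of 28 meetings will need to be recorded in order to obtain 23 meetings with each discipline", and 6.4 says "we will need to have at least 20 team encounters pre and post-CST intervention". Section 8.5 selects meetings with two or more trained clinicians.

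The SAP (Aim 2c) analyses two skills, elicitation of parental concerns and empathic response. It uses a t-test or Wilcoxon test if the score is continuous, and chi-square or Fisher if it is binary. A mixed-effects model follows only if the sample size allows and the univariate associations are significant. The SAP plans 230 meetings before and 230 after.

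**The concern.** Logistic regression with a separate intercept for each clinician estimates as many nuisance parameters as there are clinicians. When each clinician supplies only a few records, those intercepts are poorly estimated and the error carries over to the training effect. The estimated log odds ratio lies too far from zero, and the test rejects more often than its nominal level. Adding clinicians does not cure this; only more records per clinician does.

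Two things are at stake: the stated 0.05, and the size of the reported effect. The second matters more. Protocol 6.4 refers to a future stepped wedge study, and a skill effect that is too large could mislead its planning. The bias is away from zero in either direction, so a harmful effect would be exaggerated too.

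**Working it through.** **The plan's own figure.** The 0.05 is a chosen level, not a derived one, so there is nothing to reproduce. The question is what error rate the test would really have.

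**Records per clinician.** The documents do not state this number. Two routes through the Protocol's counts give a range:
- By meeting: 28 post-training meetings × 2 trained clinicians ÷ 20 clinicians = 2.8 post records each. This is a lower figure, because 8.5 sets two as a minimum. With 5 per meeting it is 28 × 5 ÷ 20 = 7.0.
- By discipline: 23 meetings per discipline, one clinician per discipline per meeting (assumed), and 20 clinicians over 4 to 6 disciplines give 23 ÷ (20/4) = 4.6 to 23 ÷ (20/6) = 6.9 post records each.

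**Large-sample size of the problem.** With T records per clinician in total, split evenly between phases, the log odds ratio is inflated by about T/(T − 1). The likelihood-ratio (LR) test then has size P(χ²₁ > 3.841 × (T − 1)/T).

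| Setting | T | Inflation | LR size |
|---|---|---|---|
| One record per phase | 2 | 2.00 | 16.6% |
| Two per phase | 4 | 1.33 | 9.0% |
| 28 + 28 meetings, 2 trained clinicians each | 5.6 | 5.6/4.6 = 1.22 | 7.6% |
| 23 + 23 per discipline, 4 disciplines | 9.2 | 9.2/8.2 = 1.12 | 6.4% |
| 23 + 23 per discipline, 6 disciplines | 13.8 | 13.8/12.8 = 1.08 | 5.9% |
| SAP's 230 + 230 meetings, 2 of the same 20 clinicians each | 46 | 46/45 = 1.02 | 5.3% |

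**Simulation with uneven attendance.** Assumptions not in the documents: trained clinicians attend at random, all 20 can be recorded in both phases, clinician SD is 1 on the logit scale, and the true log odds ratio is 0 (for error rate) or 1.0 (for bias). There were 4,000 runs per setting.

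| Meetings pre + post | Trained clinicians per meeting | Wald error | LR error | Mean estimate for a true 1.0 |
|---|---|---|---|---|
| 28 + 28 | 2 | 6.7% | 7.5% | 1.24 |
| 20 + 28 | 2 | 7.0% | 7.9% | 1.30 |
| 28 + 28 | 4 | 6.5% | 6.7% | 1.11 |

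A further simulation over 2–5 trained clinicians per meeting gave error rates of about 5–8% and mean estimates of 1.08–1.31.

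**The alternative.** In balanced simulations with 20 clinicians and 1, 2, 3, 5 or 10 records per phase, the conditional (clinician-stratified) test had an error rate of about 4–6%. The dummy-variable LR test ran from 21–22% at 1 + 1 through 8–9% at 2 + 2 to 5–6% at 10 + 10.

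**The case against.** The strongest reply is that the test is assembled from two sentences that the Protocol never joins. The fixed-effects sentence names no link, and the logistic sentence is a general line placed after the t-tests for the collaboration scale. That line cannot govern everything, because 6.3.2 also specifies linear regression and t-tests. The present-or-absent coding is explicit only in the McNemar plan for simulated meetings, and that paragraph also mentions a continuous version of each skill. A linear model on scores or counts would not have this defect. This stands, and it is why the point is conditional. Still, no other use of logistic regression is named for actual meetings, and an identifier entered as a covariate most naturally means clinician dummies.

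A reader might infer that the real error rate reaches 12–18% or more. The documents do not support that as an expected value. It needs one record per phase per clinician, while 6.3.2 speaks of multiple meetings and the Protocol's counts imply about 3 to 7 post-training records each. Within a single discipline the error can even go the other way: with 4 clinicians at 2 + 2 or 3 + 3 records, a Wald test rejects only 0.3–3% of the time, while the LR test is at 9–11%.

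It is also doubtful who is recorded before training. Protocol 3.1.3 and 4.3.1 list only clinicians outside the intervention, though the introduction to 4.3 says those to be trained are assessed. Only clinicians seen in both phases inform this model, and their number is not stated.

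Finally, the SAP's mixed model would avoid the bias. But it depends on sample size and a significant univariate result, and it covers two skills rather than the full SPIKES and NURSE set in Protocol 6.2.

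**Conclusion.** The concern holds in conditional form. If a binary skill is analysed by unconditional logistic regression with clinician dummies, the log odds ratio is inflated by about 10–30% at the Protocol's scale and the false-positive rate is about 5–8% rather than 5%. These figures rest on the assumed random attendance, recording of all 20 clinicians in both phases, and a clinician SD of 1 on the logit scale. At the SAP's meeting counts the bias would be about 2% if the same 20 clinicians recur, two per meeting. The bias in the estimate matters more than the excess over 0.05. Severity is minor: these are secondary endpoints, and the primary endpoint is qualitative.

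**What to change.** In Protocol 6.3.2 and 6.4, for skills coded present or absent, replace the identifier covariate by conditional logistic regression stratified on clinician, or by a logistic mixed model with a random clinician intercept. Name the test statistic. Keep the dummy-variable form only for continuous skill scores. Align the Protocol with the SAP's mixed model, and remove the condition that the model is fitted only after a significant univariate result. State how many clinicians are expected to be recorded in both phases.

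The cost is a change of wording; standard software fits either model and no further data are needed. One drawback is that clinicians whose outcome never varies drop out of the conditional model, but they carry no information on the training effect in the dummy-variable model either.

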3 INVESTIGATIONAL PLAN

3.1 General Schema of Study Design

This is a non-randomized cohort study with pre and post assessments around an intervention.

Clinicians and Parents Participating in Co-design of Intervention

Eligible clinicians will be approached in person and via email. If they express willingness to participate in the co-design portion of the study, they will be consented. Eligible parents of children previously hospitalized in an ICU will be approached via email or phone. If they express willingness to participate in the co-design process, they will be consented. After enrollment into the study, clinicians and parents will participate in a total of 11 sessions as focus groups to gather feedback on the CST program. Participants will be asked which aspects of the training they believe would facilitate their participation in a family meeting and sense of collaboration, which opportunities might have been missed and whether the training addressed the core competencies in collaboration. After the 11 sessions have been completed, participants will then be asked to complete a survey measuring their engagement

in the co-design process. Based on participant experience and feedback in the co-design sessions, the training will be modified to ensure its goals are met.

Clinicians Participating in Intervention

Clinicians in the CICU eligible for the intervention will be approached via email and in administrative meetings and individually consented at the beginning of the study.

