3.1.2. Co-Design of Intervention Phase

Instead of a pilot, we will conduct a co-design of the intervention with relevant stakeholders of the intervention. Experienced based co-design encourages collaborative work between vulnerable patients, their parent caregivers, and staff in complex healthcare environments¹⁰⁴, allowing for the specific needs of participants to be addressed and included in the adaptation of the intervention.¹⁰⁵ The co-design process itself impacts clinical practice due to changes in clinician behavior after participation in the co-design.¹⁰⁶ The process usually takes 9-12 months to complete and has been described as a 6 stage process: 1) setting up the project, 2) gathering staff experiences through observation and in-depth interviews, 3) gathering patient and caregiver experiences through narrative based interviews, 4) bringing staff, patients and caregivers together to share experiences of the service and shared priorities for improvement, 5) small groups of caregivers and staff working on the identified priorities, and 6) celebrating and reviewing the event.¹⁰⁴

The CST elements that will be evaluated by the co-design group will be largely modeled after the VitalTalk CST training for the ICU, named Critical Care Communication.¹⁰⁷ We will discuss the acceptability of modification of the VitalTalk CST in three ways: 1) The intervention might focus on interprofessional training rather than singularly on one profession (i.e., physicians). Exercises may be designed specifically to require teamwork in communication, highlighting the complementary skill sets of different team members. Collaboration will be emphasized and didactics will review core competencies as described by the Interprofessional Education Collaborative.⁸⁸ 2) The training may be adapted for a pediatric CICU setting while preserving several of the learning goals previously tested. We will work with [name] and pediatric CICU attending, [name], MD, to develop cases that are clinically accurate and relevant to having clinicians acquire

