3.1.3 Pre-CST Intervention Phase

Clinicians Not Participating in Intervention: Consented clinicians not participating in the intervention will be audio recorded in their previously scheduled family meetings. Clinicians not participating in the intervention will complete an online survey after the actual family meeting that they are observed participating in.

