8.4.2 Risk Assessment

Subjects Participating in Co-design: The study risks include a breach of confidentiality of responses in focus groups and survey responses. This presents no more than minimal risk of everyday life. Participation in the study will not be required for employment and others outside the research team will not be notified of an individual provider's participation in this study, including the CST co-design program. Audio recordings and transcripts from focus groups will remain confidential and will have identifying information removed at the time of transcription. Original audio files will be destroyed once transcription has been completed. All data will be collected and maintained securely as outlined in the data monitoring section. Information will be stored on password protected computers and servers. No information will be shared outside the research team and all identifying information in original audio files will be destroyed once the audio files have been transcribed and checked for accuracy, no earlier than 6 years after study completion.

Clinicians Participating in Intervention: The study risks include a breach of confidentiality of survey answers, audio and video recordings from family meetings, and/or audio and video recordings of didactic CST sessions. This presents no more than minimal risk of everyday life. Participation in the study will not be required for employment and others outside the research team will not be notified of an individual provider's participation in this study, including the CST program. Results of all surveys and audio coding will remain confidential. If subjects indicate that they would like additional emotional or professional support after completion of survey questions assessing confidence in performance of skills, referral to the employee assistance program will be suggested by the research team. There are multiple research studies and QI projects conducted in the CICU which assess clinician competency, therefore clinicians are accustomed to being interrogated about their comfort level and clinical skills and even having those skills tested as part of research. All data will be collected and maintained securely as outlined in the data

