- Speaking time will be analyzed by comparing the change in the number of words spoken by physicians versus parents speak in pre- and post-CICU TALC meetings using generalized linear regression with binomial link function controlling for the length of the meetings. Means and standard deviations will be calculated for the tool and t-tests will determine if significant differences exist for the two groups pre and post-CICU TALC.
- Elicitation of parental concerns and empathic response to parental emotion will be determined through quantitative coding. Each skill will be analyzed separately, using the cutoffs to identify skill proficiency as used by Back. Univariate relationship pre/post intervention by outcomes (Table 1)
  - If the outcomes (skills acquisition scores) are continuous and satisfies the normality assumptions, then t-tests will be appropriate to compare pre – intervention and post – intervention changes.

- If outcomes are continuous but not normally distributed, then a Wilcoxon Rank sum test will be appropriate to compare pre –intervention and post –intervention changes.
- If outcomes are binary (high vs low), then chi-square/fishers exact tests will be appropriate to compare pre –intervention and post –intervention changes.
- Similar statistical analysis will be performed to compare pre –intervention and post –intervention changes overall and for each type of participant.
- Analyses will be presented at the meeting-level as well as the participant-meeting level. Participant-meeting level data will be stratified by physician-type pending  $\geq 5$  participants in the pre- and post-intervention groups for each type.
- Relationship pre/post intervention by outcomes adjusted for participant and meeting level characteristics
  - If sample size allows and there are significant univariate associations, we will utilize mixed effect regression models to explore the relationship between the intervention and outcomes, first controlling for--gender and years of experience and accounting for correlation of repeated measurements within participants. If sample size allows, we will include other characteristics including number of participants at the meeting, proportion of speaking time by participant type, etc

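### The training effect on skills is planned as an adjusted pre/post difference that cannot be separated from unit-wide change, and the never-trained clinicians coded in both phases are not used to gauge that change

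*Protocol*

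**What the plan says.** The protocol describes its design plainly: "This is a non-randomized cohort study with pre and post assessments around an intervention" (3.1). It is run in one unit.

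**Skill analysis, protocol.** Recordings of actual meetings are to be "coded and compared to coded audio recordings from pre-intervention actual family meetings" (6.3.2). The model is "fixed-effects regression with a clinician identifier variable as a covariate so that we can examine the effect of CST intervention on skill acquisition", repeated in 6.4. The CST term is not defined, and the text does not say which clinicians enter the model.

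**Skill analysis, SAP Aim 2c.** Pre and post are compared by t, rank-sum or chi-square/Fisher tests, overall and by participant type. If sample size allows and the univariate association is significant, mixed models will "explore the relationship between the intervention and outcomes, first controlling for--gender and years of experience", with further meeting characteristics as possible additions. Stratification is by physician type, not by training status.

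**Never-trained clinicians.** Before training: "Consented clinicians not participating in the intervention will be audio recorded in their previously scheduled family meetings" (3.1.3). After training: "Actual family meeting encounters with these clinicians will be audio or video recorded and coded" (3.1.5). The Clinician Schedule of Evaluations in 5.1.1 lists SCOPE and MIPS coding for both pre-CST and post-CST actual meetings. Section 3.3.2 expects about 300 such clinicians.

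**Known differences between phases.** Sections 3.2 and 8.1.1 say that recording and data acquisition differed before and after the pandemic. Sections 5.1.1 and 6.2 survey pandemic changes to family meetings.

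Neither document names trained status, a trained-by-phase interaction, a calendar-time term or any comparison with never-trained clinicians.

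**The concern.** A clinician identifier removes stable differences between people. Gender, experience and meeting size adjust for who was present. None of these removes a shift that affects everyone between the two phases. The coefficient labelled as the CST effect is therefore the training effect plus any shared change, and the plan gives the reader no way to judge the second part.

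The stated purpose (section 2) is to assess the impact of the training on clinician behaviour. The SAP sets directional impact hypotheses, the protocol sets a two-sided alpha of 0.05, and 6.4 looks ahead to a stepped-wedge study. A pre/post change credited wholly to training could misinform that study. The data that could show the size of the shared change are already due to be coded.

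**Working it through.** **1. The plan's own figure.** Section 6.4 states 20 clinicians for 80% power at alpha 0.05, but gives no skill rates, effect size or SD, so 20 can be neither reproduced nor refuted. Solving backwards for a paired comparison:
- normal approximation: (1.960 + 0.842)/√20 = 0.626 SD of the within-clinician change;
- noncentral t: 0.660 SD.

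The value 0.66 is used in step 4.

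**2. What the coefficient estimates.** Let τ be the training effect and δ the shared change. There are two readings of the undefined CST term.
- CST = post phase. Among trainees the estimate is τ + δ. If all clinicians are pooled, it is δ plus τ diluted by the untrained share.
- CST = trained × post, with no phase term. Given clinician effects, the never-trained add nothing to the coefficient, so the estimate is again τ + δ. In one simulated dataset this model and the trainee-only pre/post model gave the same value, 0.841.

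Only a phase term together with trained × post separates τ from δ. In 3,000 simulations (assumed: 20 trained and 20 never-trained clinicians, 3 meetings each per phase, δ = 0.5, τ = 0, no spill-over), the trainee pre/post estimate averaged 0.50. The contrast averaged 0.00 and rejected in 5.1% of runs.

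**3. Size of the problem when τ = 0.** The documents state no drift, so δ is an assumed range. Inputs are two-sided alpha 0.05 (6.3.2), 28 meetings (3.1.5, taken as the number in each phase) and 230 per phase (SAP Aim 2c). For a two-sample t-test the noncentrality is δ√(n/2); for δ = 0.3 and n = 28 it is 0.3 × √14 = 1.12.

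| Shared shift (SD) | 28 per phase | 230 per phase |
|---|---|---|
| 0.2 | 11% | 57% |
| 0.3 | 20% | 89% |
| 0.5 | 45% | about 100% |

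Both columns ignore clustering of meetings within clinicians. The 230 is not reconciled with the protocol's 23 to 28, so the second column shows direction rather than a forecast. For 20 trainees compared with themselves, a shift of 0.2, 0.3 or 0.5 SD of the clinician change gives 14%, 25% or 57%.

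**4. What a trained-by-phase contrast could deliver.** Assumed: 20 trainees, equal SD of change, no spill-over, effect 0.66 SD of the clinician change. The noncentrality is 0.66/√(1/20 + 1/m), where m is the number of never-trained clinicians seen in both phases.

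| m | Power |
|---|---|
| 5 | 25% |
| 20 | 53% |
| 40 | 66% |

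The documents do not give m. With an assumed spill-over of half a 0.5 effect, the simulated contrast fell to 0.25.

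**5. Whether the contrast is estimable.** Section 4.3 says trainees' skills are assessed in actual encounters before training, alongside non-participating clinicians. Table 1 lists only post-CST encounters for trainees, and 3.1.3 names only non-participating clinicians. If Table 1 and 3.1.3 govern, a within-clinician training effect cannot be estimated, whether as a contrast or as the fixed-effects pre/post model already planned.

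**The case against.** **The never-trained are not clean controls.** This stands. Section 8.5 identifies meetings that include at least two trained clinicians, and the intervention also includes parent preparation and written summaries (1.2), which act on the whole meeting. A reader might infer that any change no larger than the never-trained clinicians' change is drift and not training. The documents do not support that, because post-phase change in the never-trained may itself be partly intervention effect.

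**The direction of bias is not assured.** This also stands. Spill-over probably dilutes the contrast. But trainees are volunteers (3.4.2.1), and the never-trained include people who were ineligible or declined (3.1). Parallel change is an assumption.

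**The same individuals may not recur.** Section 3.1 enrols never-trained clinicians for one meeting at a time and allows repeat enrolment without guaranteeing it. Group-level recording in both phases is documented; repeated observation of individuals is not.

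**Some apparent evidence of drift is weak.** A reader might cite "The co-design process itself impacts clinical practice due to changes in clinician behavior after participation in the co-design" (3.1.2). That concerns co-design participants, about 15 clinicians from units within the hospital (3.3.2), not a change shared across the CICU. Likewise "There are multiple research studies and QI projects conducted in the CICU which assess clinician competency" (8.4.2) supports the point that clinicians are used to being assessed; it does not say that communication changed. The pandemic passages are the direct evidence.

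**This is a declared pilot.** The primary endpoint is qualitative, skill change is secondary, and the SAP's adjusted model is exploratory. That limits the consequence to over-attribution in interpretation. It does not supply the missing term.

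**Conclusion.** The concern holds in a limited form. The planned estimate of the CST effect on skills in actual meetings is an adjusted pre/post difference. It cannot be told apart from a change shared by the unit, and the never-trained clinicians' coded change goes unused.

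As an illustration, shared shifts of 0.2 to 0.5 SD would give false-positive rates of about 11% to 45% at 28 meetings per phase, against a nominal 5%. Rates would be higher at 230. These figures rest on an assumed drift, equal numbers per phase and no clustering. They do not show that drift of that size occurred.

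Nor do the documents support treating a trained-by-phase contrast as the definitive answer: its power depends on an unstated number of repeat observations, and its comparison group is exposed to the intervention. This is a worthwhile, inexpensive improvement to a secondary analysis, not a flaw that undermines the primary endpoint.

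**What to change.** In Protocol 6.3.2 and 6.4 and in SAP Aim 2c:

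1. Define the CST term and state which clinicians enter the model.
2. Reconcile Table 1 and 3.1.3 with 4.3 on whether trainees have pre-CST recordings.
3. Keep the pre/post estimate, described as change associated with the CST period, which may include change shared by the unit.
4. Where trainees have recordings in both phases, add phase, trained status and trained × phase to the participant-meeting skill model. Report the interaction with its 95% CI as a supportive estimate. (With clinician fixed effects, the trained main effect is absorbed.)
5. Otherwise, report the never-trained clinicians' own pre/post change, with its CI, beside the main estimate.
6. Report how many never-trained clinicians were seen in both phases. State that spill-over probably dilutes the contrast, that volunteer selection makes parallel change an assumption, and that the direction of bias is not guaranteed.

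**Cost:** wording, one extra model and one table, with no new recordings or coding. The contrast has a wider interval: with 20 trainees and 20 never-trained clinicians its standard error is √(1/20 + 1/20)/√(1/20) = 1.41 times that of the trainee pre/post change, assuming equal SDs.
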